4.1.4.5 Rationale for Anti-PD-1 Therapy in Patients with Leptomeningeal Disease

The most common solid tumors to metastasize to the leptomeninges include: NSCLC (25.8%), breast cancer (17.7%), small cell lung cancer (16.9%) and melanoma (8.9%) ⁵⁹. The incidence of LMD by disease-specific tumor type in the era of MRI scans, is estimated at: 3.8-5% of NSCLC patients^{60,61}, 5% of breast cancer patients⁶², 2-3% of patients with metastatic melanoma⁶³, 2-10% of SCLC patients⁶⁴, and 0.03% of patients with genitourinary carcinomas⁶⁵. The incidence of LMD is also projected to be higher in patients with oncogene-addicted cancers such as NSCLCs that harbor an activating mutation in the epidermal growth factor receptor (EGFR), or a chromosomal rearrangement such as EML4-ALK, or in patients with breast cancer that harbors a HER-2 mutation. These patients appear to have a longer clinical course than those without oncogenic driver mutations, and a subset of these patients tend to develop CNS progression with LMD. The median survival for patients with LMD is estimated at 3-6 months in recently published studies 33,39,66. While this is relatively rare group of patients, there are no established treatment options for this group of patients. These patients thus constitute a critical mass with an empty therapeutic niche. This, coupled with compelling early signals of therapeutic efficacy for pembrolizumab in patients with BM as detailed above, and the fact that pembrolizumab is a generally well-tolerated therapy, makes the use of this agent in patients with LMD an exciting potential treatment option.

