4.1.5.1 Efficacy Endpoints

4.1.5.1.1 Primary Endpoint:

The primary efficacy endpoint is to evaluate CNS response with pembrolizumab in patients with LMD from solid tumors. CNS response will be defined either as radiologic response, cytologic response, or clinical response, whichever is easier to assess. Radiologic response will be defined as a reduction in size of a measurable lesion on a contrast-enhanced MRI scan of the brain. Cytologic response will be defined as a negative CSF cytology result in 2 consecutive samples, in patients who have initial positive cytology prior to treatment, or a clinical response, defined as an improvement in objective neurologic signs or symptoms attributable to LMD (Table 8). Response assessment is detailed in section 6.1.2.7.

4.1.5.1.2 Secondary Endpoints:

- **1. CNS Progression-free Survival:** A secondary endpoint of this study is to evaluate CNS-PFS, which will be defined as the time from study enrollment until CNS progression (radiologic, cytologic or clinical), or death, whichever occurs first. CNS progression will be classified as radiologic (determined by contrast-enhanced MRI scan), cytologic (determined by pathologic assessment of CSF cytology including cell count, differential, glucose) or clinical progression (defined as new objective neurologic signs or symptoms, attributable to LMD), as detailed in section 6.1.2.7.
- 2. **Overall Survival:** A secondary endpoint of this study is to evaluate OS, which will be defined as the time from study enrollment until death from any cause. Deaths from progressive disease will be stratified as related to CNS progression, related to systemic progression, or both.

8A

3. **Safety:** Safety will be evaluated according to the National Cancer Institute Common Terminology Criteria for Adverse Events (NCI CTCAE) version 4.0^{27} safety will be determined by the number of treatment-related toxicities of > grade 3 severity by CTCAE Version 4.0.

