4.3 Trial Treatments

The treatment to be used in this trial is outlined below in Table 4:

Table 4: Trial Treatment

Drug	Dose/Potency	Dose	Route of	Regimen/Treatment Period	Use
		Frequency	Administration		
Pembrolizumab	200 mg	Q3W	IV infusion	Day 1 of each 3 week cycle	Experimental

Trial treatment should begin on the day of registration or as close as possible to the date on which treatment is allocated/assigned.

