6.1.2.7 Tumor Imaging and Assessment of Response

Evaluation of response will include an evaluation of neurologic signs and symptoms (normal, improved, stable, deteriorated), CSF obtained from a previous positive site (lumbar or ventricular), and repeated radiologic evaluation of all ancillary studies (MRI Brain and Total spine with gadolinium contrast enhancement and CT scans of the body). Patients will be evaluated for CNS response based on a 4-point scale: complete response, improvement, stable disease and progression, as detailed in the Table below:

Table 8: Determination of Response to LMD

Clinical Assessment (Neurologic Function)	Size of LMD disease on MRI or CSF cytology	Overall Response Determination
No neurologic symptoms	None detectable	Complete response

Improved	Stable	Improved
Stable	Improved	Improved
Stable	Stable	Stable
Improved	Progression	Progression
Stable	Progression	Progression
Progression	Improved or Stable	Progression

We will define a positive CSF cytology result either detectable malignant cells in the CSF, or a pathology read that is reported as "suspicious for malignancy." We will define a negative CSF cytology result as either no detectable malignant cells in CSF, or a pathology read of "abnormal CSF cytology response," which will indicate conversion from positive/suspicious to negative/abnormal CSF cytology^{31,32}.

A complete responder will be defined as a patient with a normal neurologic examination, negative CSF cytology and no measurable leptomeningeal masses on radiologic imaging. Improved patients will be defined as those that have demonstrated improvement in neurologic signs or symptoms and/or a 50% decrease in CSF tumor cells or persistent positive CSF cytology as defined above, a 50% shrinkage in the bidirectional measurements of leptomeningeal disease. Patients with stable disease will be defined as less than 50% improvement in number of CSF tumor cells or abnormal CSF cytology response as defined above, or reduction in size of LMD on radiologic assessment, without evidence of progression. Progression will be defined as more than 25% increase in the number of tumor cells or persistent positive CSF cytology as defined above, an increase in size of LMD masses on radiologic assessment, or the development of new neurologic signs or symptoms after at least 2 cycles of pembrolizumab therapy.

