7.2.5. Secondary Efficacy Endpoints

1. CNS Progression-Free Survival (PFS)

PFS is defined as the time from first day of study treatment until date of progression. Progression will be stratified into CNS progression (radiologic or cytology or clinical). CNS radiologic progression will be assessed by MRI criteria, CNS cytologic progression will be determined pathologically, and neurologic progression will be determined as per section 6.1.2.7 and Table 8 respectively. PFS will be calculated using the Kaplan-Meier method.

2. Overall Survival

Overall survival will be defined as the date of study entry until date of death from any cause. Cause of death will be recorded.

3. Safety

The primary safety objective of this trial is to characterize the safety and tolerability of pembrolizumab in subjects with LMD. The primary safety analysis will be based on subjects who experienced toxicities as defined by CTCAE, Version 4.0 criteria (Appendix 2). The attribution to drug, time-of-onset, duration of the event, its resolution, and any concomitant

medications administered will be recorded. AEs will be analyzed including but not limited to all AEs, SAEs, fatal AEs, and laboratory changes. Furthermore, specific immune-related adverse events (irAEs) will be collected and designated as immune-related events of clinical interest (ECIs) as described in Section 6.2.3.2

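### CNS-PFS inherits a conflict within section 6.1.2.7: the prose does not count new neurologic signs as progression until two cycles have been given, while Table 8 sets no such limit

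*Combined protocol and SAP*

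**What the plan says.** Section 6.1.2.7 holds two rules for clinical progression.

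- **Prose below Table 8.** Progression includes "the development of new neurologic signs or symptoms after at least 2 cycles of pembrolizumab therapy".
- **Table 8.** A patient whose neurologic function has progressed while MRI or CSF cytology is improved or stable is classed overall as progression. No minimum number of cycles is given.

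Both definitions of CNS-PFS point to that section.

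- **Section 4.1.5.1.2** measures the "time from study enrollment until CNS progression (radiologic, cytologic or clinical), or death, whichever occurs first". It describes "clinical progression (defined as new objective neurologic signs or symptoms, attributable to LMD), as detailed in section 6.1.2.7". The description has no time limit of its own, but it ends by deferring to 6.1.2.7.
- **Section 7.2.5** states that "neurologic progression will be determined as per section 6.1.2.7 and Table 8 respectively", so it names the prose section and the table together.

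Section 4.9 requires discontinuation for CNS progression and cites Table 8, not the prose. Section 4.3 (Table 4) puts dosing on "Day 1 of each 3 week cycle". On prognosis, section 4.1.4.5 says: "The median survival for patients with LMD is estimated at 3-6 months in recently published studies".

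**The concern.** The prose and the table give different answers for the same patient. Take a new deficit attributable to leptomeningeal disease (LMD) at week 3, with stable MRI and CSF. Under Table 8 this is progression, and under 4.9 the patient comes off the trial. Under the prose the sign arose too early to count, so CNS-PFS has no event on that date. Two analysts who both follow the plan would date this patient differently.

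The error runs one way. Leaving out early clinical events can only delay or remove a CNS-PFS event, never advance one. It affects the patients who fail fastest. CNS-PFS is a named secondary objective with a hypothesis of improvement (section 3.2). In a single-arm trial it can be read only against outside LMD experience, so an upward shift goes straight into the interpretation.

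**Working it through.** **1. Length of the window.** Two 3-week cycles: 2 × 3 = 6 weeks. If the phrase means that two doses have been given, the window ends at the second dose, about week 3. A median survival of 3–6 months is 13.0–26.1 weeks, so 6 weeks is 6/26.1 = 23% to 6/13.0 = 46% of it.

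**2. What is observed in the window.** Section 2.1 schedules a clinical visit at each dose, and Table 7 has directed examinations at cycles 1 and 2. Early deterioration would be seen. The first on-study MRI falls between cycles 2 and 3 (6.1.2.7.2), about weeks 3–6. CSF is taken before cycle 3 (6.1.2.8.3).

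**3. Plan figures.** The plan gives no CNS-PFS median, event target or power, so there is no CNS-PFS figure to reproduce. The sample size does reproduce: 16/0.9 = 17.8, rounded up to 18. It does not depend on this point.

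**4. Events deferred (illustration).** These inputs are assumptions: exponential CNS-PFS with true median *m* of 6, 8 or 12 weeks, and a share *c* = 40–80% of early failures that are clinical and non-fatal.

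P(event before week 6) = 1 − 2^(−6/*m*). Patients deferred = 16 × P × *c*.

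| True median (weeks) | P | Deferred, of 16 |
|---|---|---|
| 6 | 0.50 | 3.2–6.4 |
| 8 | 0.41 | 2.6–5.2 |
| 12 | 0.29 | 1.9–3.8 |

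**5. Early curve.** If every deferred event lands after week 6, the 6-week CNS-PFS rate becomes 1 − P(1 − *c*). For a 6-week median the true 50% would read 1 − 0.50 × 0.6 = 70% to 1 − 0.50 × 0.2 = 90%. That is a ceiling; earlier pick-up reduces it.

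**6. Median.** The same model was simulated with three choices for what happens to a deferred event.

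| True median (weeks) | Moved to week 6 | Dated by a scan 0–4 weeks later that shows progression | Next event is death, median 4–8 weeks later |
|---|---|---|---|
| 6 | 6 | 6.6–7.0 | 7.7–10.5 |
| 8 | 8 | 8.2–8.3 | 9.3–12.0 |
| 12 | 12 | 12.0 | 12.8–15.1 |

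With a 3-week floor and death as the next event, the medians are 6.8–8.5, 8.6–10.2 and 12.3–13.6 weeks.

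**The case against.** The strongest reply is that the two-cycle clause is not the settled rule. Section 7.2.5 names Table 8 beside 6.1.2.7, and Table 8 would count the week-3 deficit. That is right, and it is why the defect is a conflict within 6.1.2.7 rather than a fixed event-free lead-in.

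A reader might also infer three stronger things, which the documents do not support.

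- **That 4.1.5.1.2 is a rival definition without a floor.** It defers to 6.1.2.7, as the SAP does, so both definitions inherit the same conflict.
- **That almost nothing except death can count before week 6.** On the natural reading the clause limits only neurologic signs. MRI is allowed from about week 3, and section 6.1 allows unscheduled procedures. The grammar could stretch the clause to every type of progression, but nothing else in the plan points that way.
- **That the median is inflated by a month or more.** That result comes from assuming that death is the next counted event. Section 6.1.2.7.3 calls for imaging at discontinuation within a 4-week window, and a scan that shows progression would remove most of the shift.

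The scan does not remove all of the problem. It is not mandatory if one was done in the previous 4 weeks. The Table 8 row in conflict is the one where MRI or CSF is improved or stable, so the scan need not show progression. Once confirmed CNS progression is recorded, 6.1.5.3.3 moves the patient to telephone survival follow-up. Both outcomes are possible, so the range should be shown.

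It is also fair to say that CNS-PFS is secondary, that Table 12 disclaims formal inference, and that the primary response endpoint at 12 weeks does not use this clause.

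**Conclusion.** The plan is wrong as written and should be fixed. The prose of 6.1.2.7 and its own Table 8 disagree on whether early clinical deterioration is progression, and both CNS-PFS definitions inherit the disagreement. That conclusion needs no modelling. A patient can be discontinued for CNS progression at week 3 and have no CNS-PFS event on that date under the prose.

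The direction of the bias is certain: upward only. Its size is not. Under the stated assumptions a 6-week floor defers about 2 to 6 of 16 patients' events and raises the early Kaplan–Meier curve. The median moves by 0 to about 1 week if a scan within 4 weeks supplies the event, and by about 1 to 4.5 weeks only if the next counted event is death. The medians, the clinical share and the delay to the next event are all assumptions; the documents give none of them.

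A reader might infer that the trial cannot proceed without this correction. The documents do not support that: no test, threshold or sample size depends on CNS-PFS.

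**What to change.** For dating the CNS-PFS endpoint, remove the two-cycle condition from the 6.1.2.7 prose so that it agrees with Table 8 and with the description in 4.1.5.1.2. Count new objective neurologic signs or symptoms attributable to LMD on the date they are first documented, from the CNS-PFS time origin onward.

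Two items should be settled in the same edit. The time origin differs: enrollment in 4.1.5.1.2, but in 7.2.5 "PFS is defined as the time from first day of study treatment until date of progression". That sentence also leaves out death, which 4.1.5.1.2 includes.

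If the two-cycle wording was meant to guide treatment decisions, the sponsor should reconcile it with Table 8 and section 4.9 separately. No treatment rule is proposed here.

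The cost is one clause. The examinations are already scheduled, and no visits, tests or patients are added. Reported CNS-PFS becomes slightly less favourable.

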6.1.2.7.1. Initial Tumor Imaging

Initial tumor imaging and screening should be performed within 28 days prior to the date of allocation. The site study team must review screening images to confirm the subject is assessable for response based on MRI, CSF cytology or clinical presentation, as detailed in Table 8.

Tumor imaging performed as part of routine clinical management are acceptable for use as initial tumor imaging if they are of diagnostic quality, include all anatomy as described in the SIM, and performed within 28 days of the date of allocation.

6.1.2.7.2. Tumor Imaging During the Trial

The first on study imaging assessment should be performed anytime between cycle 2 and 3 of planned therapy, and the second set of imaging should be performed anytime between cycle 4 and 5. In patients who only receive the planned 4 doses of therapy, this is replaced with the end of treatment MRI and CT, which should be done within 2 weeks of the last dose of therapy. Subsequent tumor imaging should be performed Q9W (±7 days) or more frequently if clinically indicated until PD. Imaging should not be delayed for delays in cycle starts or extension of pembrolizumab cycle intervals.

To assess radiologic response in the CNS, there are no standard radiologic response criteria for LMD on CT or MRI. The RANO group has proposed criteria for measuring BM⁷⁷, but not for LMD. From an extensive review of published literature of clinical trials and assessments of LMD in the modern MRI era^{33,78}, we propose using a radiologic cut-off of 3mm for measurable disease in the neuro-axis by gadolinium-enhanced MRI imaging of the brain and total spine including T1- weighted, T2-weighted, fluid attenuated inversion recovery and post-gadolinium sequences.

To assess for response outside of the CNS, per RECIST 1.1, partial or complete response should be confirmed by a repeat tumor imaging assessment not less than 4 weeks from the date the response was first documented. The tumor imaging for confirmation of response may be performed at the earliest 4 weeks after the first indication of response, or at the next scheduled tumor imaging (i.e. 9 weeks later), whichever is clinically indicated. Subjects will then return to regular scheduled imaging Q9W, starting with the next scheduled imaging time point. Subjects who obtain a confirmation imaging assessment do not need to undergo scheduled tumor imaging if it is < 4 weeks later and may wait until the next scheduled imaging time point.

Per irRECIST, if radiologic imaging identifies PD, tumor assessment should be repeated ≥ 4 weeks later in order to confirm PD with the option of continuing treatment while awaiting radiologic confirmation of progression. Subjects who obtain confirmation tumor imaging do not need to undergo scheduled tumor imaging if it is < 4 weeks later and may wait until the next scheduled imaging time point if clinically stable.

Imaging should continue to be performed until either CNS progression as per Table 8, withdrawal of consent, death, or notification by the Sponsor, whichever occurs first.

If the subject is clinically stable but has radiologic PD outside of the CNS, it is the discretion of the PI to continue to treat and image the subject at least 4 weeks after the first tumor imaging indicating PD by RECIST 1.1 by the site. irRECIST would then be followed by the study site to determine if the follow-up tumor imaging confirms PD (irPD). Subjects who have unconfirmed PD may continue on treatment and follow the regular imaging schedule intervals until subsequent PD (irPD) is confirmed by the site per irRECIST provided they

have met the conditions detailed in Section 6.1.2.7.5 (Table 8).

6.1.2.7.3. End of Treatment and Follow-up Tumor Imaging

In subjects who discontinue trial treatment, tumor imaging should be performed at the time of treatment discontinuation (\pm 4 week window). If a previous CT scan for body imaging and MRI for CNS imaging was obtained within 4 weeks prior to the date of discontinuation, then a scan at treatment discontinuation isn't mandatory.

6.1.2.7.4 RECIST 1.1 Assessment of Disease

RECIST 1.1 will be applied as an assessment of systemic tumor response outside the CNS.

During the follow-up period, imaging will be repeated every Q9W (± 7 days) until PD. See the Trial Flow Chart for further information.

6.1.2.7.5 Immune-related RECIST

RECIST 1.1 will be adapted to account for the unique tumor response characteristics seen with treatment of pembrolizumab. Immunotherapeutic agents such as pembrolizumab may produce anti-tumor effects by potentiating endogenous cancer-specific immune responses. The response patterns seen with such an approach may extend beyond the typical time course of responses seen with cytotoxic agents, and cam manifest a clinical response after an initial increase in tumor burden or even the appearance of new lesions. RECIST may not provide an accurate response assessment of immunotherapeutic agents such as pembrolizumab. Immune-related RECIST (irRECIST) is RECIST 1.1 adapted as described below to account for the unique tumor response seen with immunotherapeutics. Following site identification of PD, irRECIST will be used by site investigators to assess tumor response and progression and make treatment decisions.

If radiologic imaging by the site identifies PD by RECIST 1.1, imaging should be repeated >4 weeks later in order to confirm PD with the option of continuing therapy per below while awaiting radiologic confirmation of progression.

If repeat imaging shows <20% tumor burden compared to nadir, stable or improved previous new lesion (if identified as cause for initial PD), and stable/improved non-target disease, if identified as cause of initial PD), PD is not confirmed. Treatment may continue and subsequently follow the regular imaging schedule.

If repeat imaging confirms PD (irPD) due to any of the scenarios listed below, this will be recorded. However, pembrolizumab may be continued in patients if they have not demonstrated CNS progression, as detailed in Table 8, at the discretion of the treating investigator.

If determining whether or not the tumor burden has increased or decreased, site study team should consider all target lesions as well as non-target lesions.

Scenarios where PD is confirmed at repeat imaging:

- Tumor burden remains >20% and at least 5mm absolute increase compared to nadir
- Non-target disease resulting in initial PD is worse (qualitative)
- New lesion resulting in initial PD is worse (qualitative)
- Additional new lesion(s) since last evaluation
- Additional new non-target progression since last evaluation

In subjects who have initial evidence of radiologic PD by the site, it is at the discretion of the site investigator whether to continue the subject of study treatment, until repeat imaging is obtained. This clinical judgment decision should be based in the subject's overall clinical condition, including performance status, clinical symptoms, and laboratory data. Subjects may receive study treatment while waiting for confirmation of PD if they are clinically stable, as defined by the following criteria:

- Absence of symptoms and signs indicating clinically significant progression of disease including worsening laboratory values
- No decline in ECOG performance status
- Absence of rapid progression of disease
- Absence of progressive tumor at critical anatomical sites (e.g. spinal cord compression) requiring urgent alternative medical intervention

When feasible subjects, radiologic progression should be confirmed. This takes into account the observation that some subjects can have transient tumor flare in the first few months after the start of immunotherapy, but with subsequent disease response. Subjects that are deemed clinically unstable are not required to have repeat imaging for confirmation of PD.

Pembrolizumab may be continued in patients with radiologic PD in the body if a subject is clinically stable and has not demonstrated CNS progression, as detailed in Table 8 and Table 9, at the discretion of the treating investigator.

These details are summarized in Table 9, below.

Table 9: Imaging and Treatment after First Radiologic Evidence of PD

	Clinically Stable		Clinically Unstable	
	Tumor imaging	Treatment	Tumor imaging	Treatment
1 st radiologic evidence PD	Repeat tumor imaging at > 4 weeks at site to	May continue study treatment at the local site	Repeat tumor imaging at > 4 weeks to	Discontinue treatment

	confirm PD	investigator's discretion while awaiting confirmatory tumor imaging by site	confirm PD per physician discretion only	
Repeat imaging confirms PD	No additional tumor imaging required	May continue treatment, at discretion of treating investigator	No additional tumor imaging required	Discontinue treatment
Repeating imaging show SD, PR, CR	Continue regularly scheduled tumor imaging assessments	Continue study treatment at the local site investigator's discretion	Continue regularly scheduled tumor imaging assessments	May restart study treatment if condition has improved and/or clinically stable per local site investigator's discretion

- In determining whether or not the tumor burden has increased or decreased, local study site investigators should consider all target lesions as well as non-target lesions as per irRECIST. Subjects that are deemed clinically unstable are not required to have repeat tumor imaging for confirmation.
- For a clinically stable subject with first radiologic evidence of PD (i.e., unconfirmed progression of disease), it is at the discretion of the site investigator to continue treating the subject with the assigned treatment per protocol until progression of disease is confirmed at least 28 days from the date of the tumor imaging first suggesting PD. Pembrolizumab may be continued in patients if they have not demonstrated CNS progression, as detailed in Table 8, at the discretion of the treating investigator.

irRECIST data will be collected in the clinical database.

